8.3.6.4. Renal Complications

If renal complications develop, participants should be closely monitored for disturbances in creatinine clearance. Additional investigations can be performed at the investigator's discretion. Participants must be treated as clinically appropriate.

Participants who develop confirmed grade 3 or 4 eGFR abnormalities with reduction from baseline by at least 10 mL/min/1.73 m² will permanently discontinue the intake of JNJ-3989 and JNJ-6379 (or placebos) if considered at least possibly related to JNJ-3989 or JNJ-6379 and should be followed appropriately until resolution of the AE or toxicity. Rechallenge is not allowed. Change of NA treatment should be considered according to the prescribing information.

8.3.6.5. Hematologic Abnormalities

Mild thrombocytopenia was observed in recently conducted non-clinical toxicology studies with the combination of JNJ-3989 and JNJ-6379. In addition, in a 3-month combination study with 80 rats, 1 rat developed pancytopenia related to bone marrow depletion after 23 days of dosing. Previously, in a 9-month dog study in 24 dogs treated with JNJ-6379 alone, pancytopenia which correlated with a marked increase in plasma cell-like cells in the bone marrow was observed in 1 dog after 60 days of dosing.

No thrombocytopenia or pancytopenia has been observed in the ongoing Jade study (56136379HPB2001) investigating JNJ-6379/Placebo with or without NA treatment. All 232 participants have completed at least 24 weeks of study treatment. In the Phase 1/2a AROHBV1001 study with JNJ-3989, mild transient thrombocytopenia (Grade 1) was observed in 6 out of 84 participants receiving 3 SC injections of JNJ-3989 alone over a period of up to 12 weeks with background of NAs. The transient thrombocytopenia was not considered clinically significant. No thrombocytopenia or pancytopenia was observed in 12 patients when JNJ-3989 and JNJ-6379 were given in combination over a 12-week period.

Based on the non-clinical findings, any relevant abnormalities in hematologic parameters will be carefully monitored as described below:

- Platelet counts: <100,000 cells/mm³ or <100 G/L or reduction from baseline by at least 50%
- Hemoglobin: Decrease of at least 2 g/dL from baseline or at least Grade 2 (DAIDS)
- Reticulocytes: Reduction to <0.5% of the RBC count
- Neutrophil count: Treatment emergent reduction to at least Grade 2 (DAIDS)

In case any one of the above criteria are met, a confirmatory visit should be scheduled as soon as possible, preferably within 7 days of the receipt of the initial results. Confirmation of the results will trigger weekly or biweekly (every other week) unscheduled visits until improvement or stabilization of the respective parameter(s). Stabilization is defined as no further significant reduction over two consecutive visits.

In case of confirmed Grade 3 or Grade 4 hematologic abnormalities, discontinuation of investigational study treatment (JNJ-3989 and/or JNJ-6379/placebo) should be considered. In case of discontinuation, NA treatment should be continued.

8.4. Treatment of Overdose

For this study, any dose of JNJ-3989 and JNJ-6379 greater than the protocol-specified dose (refer to Section 6.1) will be considered an overdose; any dose of NA (ETV, TDF or TAF) greater than the prescribed dose will be considered an overdose. The sponsor does not recommend specific intervention for an overdose.

In the event of an overdose, the investigator or treating physician should:

- Contact the Medical Monitor immediately.
- Closely monitor the participant for AE/SAE and laboratory abnormalities.
- Obtain a plasma sample for PK analysis as soon as possible from the date of the last dose of study intervention if requested by the Medical Monitor (determined on a case-by-case basis).
- Document the quantity of the excess dose as well as the duration of the overdosing in the CRF.

Decisions regarding dose interruptions will be made by the investigator in consultation with the Medical Monitor based on the clinical evaluation of the participant.

8.5. Pharmacokinetics

Plasma samples will be used to evaluate the PK of the study intervention. Samples collected for analyses of the study intervention's plasma concentrations may additionally be used to evaluate safety or efficacy aspects.

All participants will have sparse PK sampling on Day 1 and at Weeks 4, 12, and 24 (and at early withdrawal). All participants who consent to participate in the intensive PK subgroup (optional) will undergo intensive PK sampling at Week 4 (minimally 18 participants). If necessary (eg, for operational reasons), this visit may be scheduled at Week 8, 12, or 16.

Plasma concentration-time data for JNJ-3989 (ie, JNJ-3976 and JNJ-3924), JNJ-6379 and, optionally, NA will be analyzed via population PK for all participants. Area under the plasma concentration-time curve over 24 hours (AUC_{24h}) and plasma trough concentrations (C_{0h}) will be estimated using empiric Bayes estimation.

Plasma concentration-time data for JNJ-3989 (ie, JNJ-3976 and JNJ-3924), JNJ-6379 and, optionally, NA will be analyzed via noncompartmental methods for all participants who underwent intensive PK sampling. The main PK parameters will be AUC_{24h} , C_{max} , t_{max} , C_{0h} , plasma concentration at the end of the dosing interval (τ) (C_τ), and minimum plasma concentration (C_{min}). Additional exposure parameters may be calculated if applicable.

Data from this study may be combined with other studies via population PK modelling to enable the calculation of the above PK parameters also in participants who only underwent sparse PK sampling.

8.6. Pharmacokinetic/Pharmacodynamic Evaluations

Relationships of individual PK parameters (intensive PK and population PK, as applicable) for JNJ-3989 (ie, JNJ-3976 and JNJ-3924), JNJ-6379, and NA, as applicable, with selected efficacy and safety endpoints will be evaluated.

8.7. Immune Assessments

At selected sites, PBMC samples for immune analyses will be collected during study intervention and follow-up and will be analyzed centrally for HBV-specific responses by enzyme-linked immunospot (ELISpot) and/or intracellular cytokine staining (ICS) after stimulation with HBV-specific antigens. ELISpot detects T-cells that secrete gamma interferon (IFN- γ) in response to a specific antigenic stimulation, whereas ICS determines the frequency of CD4+ and CD8+ T-cells secreting cytokines such as IFN- γ , interleukin (IL)-2 and tumor necrosis factor (TNF)- α in response to a specific antigenic stimulation.

Additional experiments may be performed to further phenotypically and functionally characterize PBMCs using proliferation or cytotoxic assays or other methods such as cytometry by time of flight to evaluate innate and adaptive immune responses. Leftover PBMC samples may be used at the sponsor's discretion for additional exploratory research related to HBV infection or study intervention (safety/efficacy).

Additional PBMC samples may be taken in case of ALT flares, upon discussion with the sponsor, which may require an unscheduled visit.

8.8. Host Genetics

A pharmacogenomic (host DNA) blood sample should be collected at baseline to allow for host pharmacogenomic research, where local regulations permit. In addition, host DNA blood samples to allow for epigenetic analyses will be collected. These samples could for example be used to assess changes in frequencies of immune cells such as myeloid derived suppressor cells. These samples will only be collected from participants who consent separately to this component of the study. Complete host genomic testing may be done to search for links of specific genes to (HBV-related) liver disease or to the PK, PD, efficacy, safety, or tolerability of the study intervention. Only host DNA research related to the study interventions under this protocol or to chronic HBV infection will be performed. Further, a participant may withdraw such consent at

any time without affecting their participation in other aspects of the study, or their future participation in the Platform study (see Section 7.2.1 of the Master Protocol PLATFORMPAHPB2001).

In addition, other samples may be used for exploratory genetic or epigenetic research in participants consenting separately to this part of the study. No genetic research will be performed on any sample in participants who have not provided the additional separate consent for host genetic research. These samples can only be used to investigate the potential association of genetic or epigenetic factors with efficacy, safety, or PK of the study intervention, or HBV infection, or may be used to develop tests/assays related to the study intervention or HBV infection.

These analyses will be performed at the sponsor's discretion, will always be under the sponsor's supervision, and may be reported separately.

8.9. Exploratory Host Biomarkers

The study includes collection of blood samples for exploratory analysis of host blood biomarkers at the host RNA, protein, and cell level. Sampling will be performed at the time points indicated in the [Schedule of Activities](#). Leftovers of other samples might also be used for exploratory research of host and viral markers.

Samples can only be used for research related to study intervention or HBV infection or may be used to develop tests/assays related to study intervention or HBV infection.

Blood samples will be taken at the time points indicated in the [Schedule of Activities](#) which can be used to explore immunogenicity of JNJ-3989. The emergence of antibodies to JNJ-3989 (antidrug antibodies) might be analyzed using assays such as an enzyme-linked immunosorbent assay.

These analyses will be performed at the sponsor's discretion, will always be under the sponsor's supervision, and may be reported separately from the main study report.

More information is provided in Section 8.8 of the Master Protocol PLATFORMPAHPB2001.

9. STATISTICAL CONSIDERATIONS

Statistical analysis will be done by the sponsor or under the authority of the sponsor. A general description of the statistical methods to be used to analyze the efficacy and safety data is outlined below. Specific details will be provided in the Statistical Analysis Plan (SAP).

9.1. Statistical Hypothesis

The primary hypothesis of this study is that the combination regimen of JNJ-3989+JNJ-6379+NA is more efficacious than NA treatment alone, as measured by the primary efficacy endpoint, the proportion of participants with HBsAg seroclearance at Week 72 (ie, 24 weeks after completion of all study interventions at Week 48) without restarting NA treatment.

9.2. Sample Size Determination

The total study sample size is 120 participants who will be randomly assigned to one of the two intervention arms in a 2:1 ratio (JNJ-3989+JNJ-6379+NA: placebo+placebo+NA). Statistical power to test the primary hypothesis was assessed using the Mantel-Haenszel test with a 1-sided Type 1 error rate of 0.05, assuming the observed percentage of participants with HBsAg seroclearance at Week 72 in the placebo+placebo+NA arm to be 5%. The sample size of 80 participants in the investigational arm and 40 participants in the control arm provides >91% statistical power to detect a $\geq 20\%$ difference in the primary endpoint.

The 2:1 randomization ratio (N 80:40, JNJ-3989+JNJ-6379+NA:placebo+placebo+NA) was chosen to balance statistical and clinical considerations as it provides adequate evidence of efficacy and safety, with the benefit of offering study participants a higher chance to receive investigational treatment. Safety will be compared between arms descriptively only, and no inferential testing is planned.

9.3. Populations for Analyses

For purposes of analysis, the following populations are defined:

Population	Description
Screened	All participants who signed the ICF for the Master Protocol and this ISA
Enrolled	All participants who were randomly assigned to an intervention arm in this ISA
Intent-to-treat (ITT)	All participants who were randomly assigned to an intervention arm and who received at least 1 dose of study intervention within this ISA. Participants will be analyzed according to the study intervention they were randomly assigned to.
Safety	All participants who received at least 1 dose of study intervention within this ISA. Participants will be analyzed according to the study intervention they actually received.

9.4. Statistical Analyses

9.4.1. Efficacy Analyses

The primary efficacy analysis will be performed when all participants have completed Week 72 or discontinued earlier. The final analysis will be performed when all participants have completed the last study visit (Week 96) or discontinued earlier.

To evaluate the efficacy, the primary analysis set will be the Intent-to-treat (ITT) population (defined in Section 9.3).

All efficacy summaries will be presented with descriptive statistics by intervention arm. If the endpoint is continuous, the descriptive statistics will include the number of participants, mean, standard deviation (SD), median, range and interquartile range. If the endpoint is binary or categorical, the frequency distribution with the number and percentage of participants in each category will be calculated. For time-to-event variables, a summary table including number of participants included in the analysis, number of participants censored, 25th and 75th percentiles and median time-to-event will be shown by intervention arm. Graphic displays will also be used to summarize the data. Summaries will also be presented by randomization stratification factors,

screening HBsAg level (<1,000 IU/mL or \geq 1,000 IU/mL), race (Asian versus non-Asian) and type of NA (TDF/TAF versus ETV).

The baseline measurements are defined as the measurements taken closest to but before the first administration of study intervention on Day 1.

9.4.1.1. Primary Efficacy Endpoint (HBsAg Seroclearance 24 Weeks After Completion of All Study Interventions at Week 48)

The proportion of participants who achieved HBsAg seroclearance at Week 72 (24 weeks after completion of 48 weeks of treatment with study interventions) without restarting NA treatment will be compared between intervention arms at a 1-sided 0.05 alpha. The primary endpoint will be compared between intervention arms using the stratum-adjusted Mantel-Haenszel difference in proportions,²⁵ where the stratification factors screening HBsAg level (<1,000 IU/mL or \geq 1,000 IU/mL), race (Asian versus non-Asian) and type of NA (TDF/TAF versus ETV) determine the strata. The associated 90% confidence interval (CI) for the difference in proportions will also be calculated.

All participants who do not achieve HBsAg seroclearance at Week 72 and/or require NA re-treatment between Week 48 and Week 72 are considered treatment non-responders for the purpose of the primary endpoint analysis. In addition, participants who withdraw from treatment prior to Week 48 or from the study prior to Week 72 will be defined as non-responder. If the HBsAg value at Week 72 is missing, the non-missing value closest to Week 72 within the window of Weeks 60-84 (12 weeks prior/after Week 72) will be used.

Additional analyses may be performed on the primary efficacy endpoint using the Bayesian methodology to leverage the Platform framework. Posterior probabilities will be calculated for the treatment difference in the primary efficacy endpoint. This Bayesian analysis may incorporate historical data and/or data from other ISAs that may enter the Platform study in the future. Details on the Bayesian approach will be provided in the Modelling and Simulation Report.

9.4.1.2. Secondary and Exploratory Efficacy Endpoints

Descriptive statistics will be used for all efficacy endpoints which will be summarized by intervention arm and study phase. Comparisons between intervention arms will be done with no adjustment for multiplicity. Specific key selected endpoints may be analyzed using suitable categorical data approaches (eg, Cochran-Mantel-Haenszel or logistic regression for proportions or other categorical type of endpoint), longitudinal repeated measures models (eg, for continuous types of variables), or survival analysis based on the Kaplan-Meier estimates (for time-to-event variables), as appropriate. Details will be described in the SAP.

To evaluate the efficacy at the end of treatment, the proportion of participants with HBsAg seroclearance and the proportion of participants with HBV DNA <LLOQ at Week 48, respectively, will be tabulated by study intervention arm. Between arm comparisons for both endpoints will be evaluated using the stratum-adjusted Mantel-Haenszel difference in

proportions, where the stratification factors screening HBsAg level (<1,000 IU/mL or \geq 1,000 IU/mL), race (Asian versus non-Asian) and type of NA (TDF/TAF versus ETV) determine the strata and corresponding 90% cIs.

The efficacy of the study intervention during the follow-up phase will also be evaluated. The proportion of participants with HBsAg seroclearance at Week 96 without restarting NA treatment, the proportion of participants with HBV DNA <LLOQ at Weeks 72 and 96, respectively, the proportion of participants achieving partial response (HBV suppression without restarting NA treatment) at different time points during follow-up, the proportion of participants with flares (virologic, biochemical, and clinical), and the proportion of participants requiring NA re-treatment during follow-up will be tabulated by intervention arm. The comparison between the intervention arms will be done using the stratum-adjusted Mantel-Haenszel difference in proportions, as described above. A similar analysis will be conducted for the proportion of participants with HBsAg seroclearance 24 and 48 weeks, respectively, after stopping all study interventions without restarting NA treatment.

The proportion of participants who reach HBV DNA <LLOQ and/or ALT normalization after restart of NA treatment during follow-up will also be tabulated by intervention arm and the comparison between the intervention arms will be done using the Mantel-Haenszel test for difference in proportions as described above.

The blood markers (such as HBsAg, HBV DNA, and ALT) during study intervention and follow-up will also be summarized by intervention arm over time and plotted. The proportion of participants with virologic breakthrough (on treatment) and the proportion of participants with (sustained) reduction, suppression, and/or seroclearance during follow-up considering single and multiple markers (such as HBsAg, HBV DNA, and ALT) will be summarized by intervention arm. The proportion of participants with HBsAg seroconversion will be tabulated by intervention arm. Descriptive statistics on values and changes from baseline over time in HBsAg and HBV DNA will be summarized by intervention arm. Additional summaries will be provided by the randomization stratification factors (screening HBsAg level [$<1,000$ IU/mL or \geq 1,000 IU/mL], race [Asian versus non-Asian] and type of NA [TDF/TAF versus ETV]).

The time to achieve first HBsAg seroclearance will be summarized based on Kaplan-Meier estimates in tables and graphs and compared between study interventions using the log rank test. The proportion of participants with HBsAg levels and/or changes from baseline below/above different cut-offs, and the proportion of participants with HBV DNA levels and/or changes from baseline below/above different cut-offs will be analyzed as appropriate by intervention arm and over time. The proportion of participants with ALT decrease and normalization will be tabulated by intervention arm.

Graphic data displays will also be used to summarize the efficacy data by intervention arm and over time.

In addition, the potential association between treatment outcome and baseline factors (including but not limited to screening HBsAg level [$<1,000$ IU/mL or \geq 1,000 IU/mL], race [Asian versus

non-Asian] and type of NA [TDF/TAF versus ETV], and other HBV and host characteristics) will be explored by multivariate analyses and exploration of interaction terms.² Exploratory subgroup summaries will be displayed graphically in forest plots.

9.4.1.3. Resistance Analyses

The results of HBV viral sequencing will be evaluated by the sponsor virologist. Relevant changes of amino acid and/or nucleic acid variations (eg, substitutions) in the HBV genome will be tabulated and described.

Additional exploratory characterization of the HBV viral sequence and phenotype may be performed and reported separately.

9.4.1.4. Patient-reported Outcomes

The PRO scores will be analyzed descriptively as mean scores over time, and (if applicable) evaluated based on the proportion of participants experiencing a clinically important improvement or worsening in PRO scores from baseline during study intervention and follow-up. Analyses will also be performed on PRO score changes from baseline at specific time points (Weeks 48, 72, 96) and between Week 48 and later time points for different subgroups: participants with HBsAg seroclearance 24 weeks and 48 weeks after completion of all study interventions at Week 48 without restarting NA treatment versus those without HBsAg seroclearance at those time points. Further details will be provided in the SAP.

The data collected in this study will be used to assess the psychometric properties of the HBV-specific self-stigma scale. The psychometric analyses will be described in a separate document and results will be presented in a separate report.

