5.3.1.1.1. HBsAg Sero clearance

Sero clearance of HBsAg is defined as HBsAg level <LLOQ. HBsAg sero clearance may be achieved prior to the time point assessed but must be observed at the given week of interest.

HBsAg sero clearance will be evaluated over all time points when assessed, with emphasis at the following time points:

- at Week 48
- at Week 96 (ie, 48 weeks after completion of all study interventions at Week 48) without restarting NA treatment,
- 24 weeks after stopping all study interventions (regardless when intervention was stopped) without restarting NA treatment, and
- 48 weeks after stopping all study interventions (regardless when intervention was stopped) without restarting NA treatment

If the HBsAg value at Week 48 is missing, the LOCF approach will be used with the condition that no value earlier than Week 40 may be carried forward.

For the analyses of sero clearance 24 and 48 weeks after stopping all study intervention respectively, participants with HBsAg sero clearance at the respective time points, and without restarting NA treatment will be considered as having achieved this endpoint. If HBsAg values are missing, then LOCF in conjunction with the next available observation (if available for 48 weeks after stopping all study interventions) imputation approach will be used. The available non-missing HBsAg value closest to the time point which is no earlier/later than 12 weeks prior/after to the respective time point will be used.

For the analyses of sero clearance at Week 96 participants with HBsAg sero clearance at the respective time points, and without restarting NA treatment will be considered as having achieved this endpoint. If HBsAg values are missing, then LOCF approach will be used. The available non-missing HBsAg value closest to the time point which is no earlier than 12 weeks prior to the respective time point will be used.

For all other time points, seroclearance will be analyzed as observed case without imputation.

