9.1.2. Analysis Methods

Descriptive statistics of the actual values and change from baseline values at each timepoint (including baseline and available analysis time point) for the scores will be displayed for each aspect by intervention arm. The proportion of participants experiencing a clinically important improvement or worsening from baseline (if applicable) at each timepoint will be calculated by intervention arm. Analyses will also be performed on the changes from baseline at specific time points as appropriate for different subgroups: participants with versus participants without HBsAg seroclearance 24 weeks and 48 weeks after completion of all study intervention at Week 48.

In addition, effect sizes will be calculated to measure the magnitude of difference between means in all different intervention arms using an ANCOVA, with intervention arm, and 3 randomization stratification factors, as main effect in the model, and the three 2-way intervention arm-stratification factor interaction terms, and baseline as covariate. The LS means of the change from baseline on the analysis time points with estimates, SE, 90% CI, p-values will be presented. A graphical representation may be used to display the adjusted mean change from baseline.

9.2. 5-Level EuroQol 5-Dimension Questionnaire

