9.2.2. Analysis Methods

For the EQ-5D descriptive system, descriptive statistics on the actual value and change from baseline will be presented.

For the EQ-5D VAS and for the Valuation index, descriptive statistics for the actual and change from baseline values at each time point will be displayed. In addition, mean changes from baseline will be explored per subgroup: participants with versus participants without HBsAg seroclearance 24 weeks and 48 weeks after completion of all study intervention at Week 48. The clinically

important thresholds of 7 and 10 will be used to interpret the mean change from baseline in the VAS.

The number (and percentage) of participants with clinically important improvement/ worsening will be presented for EQ-5D VAS:

- Clinical Important Improvement = change from baseline ≥ 7 , and also for ≥ 10
- Clinical Important Worsening = change from baseline ≤ -7 , and also for ≤ -10 .
- Other changes from baseline values are categorized as ‘No Clinically Important Change’.

A cumulative distribution function of the EQ-5D VAS will be drawn at different time points (baseline and changes from baseline).

REFERENCES

Bourne, C. R., Finn, M. G., & Zlotnick, A. (2006). Global structural changes in hepatitis B virus capsids induced by the assembly effector HAP1. *Journal of virology*, 80(22), 11055-11061.

Honaker J, King G et al.. Amelia II: A Program for Missing Data. *Journal of Statistical Software*, 45, 7, Pp. 1-47.

Katen, S. P., Tan, Z., Chirapu, S. R., Finn, M. G., & Zlotnick, A. (2013). Assembly-directed antivirals differentially bind quasiequivalent pockets to modify hepatitis B virus capsid tertiary and quaternary structure. *Structure*, 21(8), 1406-1416.

King G., Honaker J., Joseph A., et al. Analyzing Incomplete Political Science Data: An Alternative Algorithm for Multiple Imputation. *American Political Science Review*, Vol. 95:49-69.

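### The SAP's PRO comparison by HBsAg seroclearance drops the protocol's no-NA-restart condition and its change from Week 48

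*Protocol*

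**What the plan says.** Protocol section 9.4.1.4 (the synopsis agrees) sets two contrasts for the PRO scores: "changes from baseline at specific time points (Weeks 48, 72, 96) and between Week 48 and later time points for different subgroups". The responder group is defined by HBsAg seroclearance 24 and 48 weeks after all interventions are completed at Week 48, and the comparison is "without restarting NA treatment versus those without HBsAg seroclearance at those time points". The section then hands over: "Further details will be provided in the SAP".

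The SAP treats the two instruments separately.

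- Self-stigma scale, section 9.1.2: "Analyses will also be performed on the changes from baseline at specific time points as appropriate for different subgroups", the subgroups being "participants with versus participants without HBsAg seroclearance 24 weeks and 48 weeks after completion of all study intervention at Week 48".
- EQ-5D VAS and index, section 9.2.2: "mean changes from baseline will be explored per subgroup: participants with versus participants without HBsAg seroclearance", at the same two time points.

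Neither SAP section mentions NA restart or a change from Week 48. SAP section 5.3.1.1.1 says that seroclearance "of HBsAg is defined as HBsAg level <LLOQ", with no reference to NA.

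**The concern.** The protocol left detail to the SAP, but on this point the SAP says less than the protocol, and it does so for both instruments. Two things follow.

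- **Group membership.** A participant who stopped NA at Week 48, restarted it, and is HBsAg <LLOQ at Week 72 or 96 meets the SAP's rule for the seroclearance group. The protocol keeps that person out. The SAP's own functional-cure definition (section 5.2.1) would not count that person as a responder either.
- **Contrast.** All interventions stop at Week 48. A change from baseline to Week 72 or 96 combines 48 weeks of injections and daily tablets with the period off treatment. The protocol's second contrast, from Week 48 onward, separates them. The SAP omits it.

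At stake is whether the exploratory PRO comparison is the one the protocol describes.

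**Working it through.** The plan gives no figure to reproduce here, so the check is mainly a comparison of texts.

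| Element | Protocol 9.4.1.4 | SAP 9.1.2 | SAP 9.2.2 |
|---|---|---|---|
| Change from baseline | Weeks 48, 72, 96 | Yes, weeks not named | Yes, weeks not named for the subgroups |
| Change from Week 48 | Yes | No | No |
| Responder group | Seroclearance and no NA restart | Seroclearance | Seroclearance |
| Comparator | No seroclearance | No seroclearance | No seroclearance |

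**Can the no-restart condition be read into the SAP's term?** The definition in section 5.3.1.1.1 is HBsAg <LLOQ alone. Where the SAP wants the condition it writes it out: for the primary endpoint (5.2.1), and for seroclearance at Week 96 and at 24 and 48 weeks after stopping (5.3.1.1.1 and 5.3.2.1). It does not attach it to seroclearance at Week 48. The term therefore does not carry the condition, and the PRO sections do not cross-refer to the endpoints that do.

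**Is the change from Week 48 covered elsewhere?** Section 5.3.1.2 plans changes from EOT and from Week 48 in follow-up, but only for HBsAg. The SAP's Amendment 1 table records that addition. It lists no PRO change and gives no reason for leaving the PRO contrast out.

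**Are the data collected?** The protocol's schedules of activities place both PRO instruments at Week 48 and at four follow-up visits. The extracted follow-up table is broken, so the exact weeks should be confirmed there; section 9.4.1.4 itself names Weeks 72 and 96.

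**What can be recovered from the SAP's tables?** For the same participants,

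mean(W72 − baseline) − mean(W48 − baseline) = mean(W72 − W48).

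The mean off-treatment change can be obtained by subtraction if the Week 48 and later subgroup summaries are both shown and cover the same people. Its spread cannot, because

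Var(W72 − W48) = Var(W72 − baseline) + Var(W48 − baseline) − 2 Cov(W72 − baseline, W48 − baseline),

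and the covariance is not tabulated.

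**How large could the group change be?** The sample-size section takes 5% in the control arm of 40 and a difference of 20 points, hence 25% in the investigational arm of 80:

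0.25 × 80 + 0.05 × 40 = 20 + 2 = 22 responders.

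If k participants who restarted NA are also HBsAg <LLOQ, they make up k / (22 + k) of the SAP's group:

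- k = 1: 1/23 = 4%
- k = 3: 3/25 = 12%
- k = 5: 5/27 = 19%
- k = 10: 10/32 = 31%

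The documents do not give k. These values are an illustrative range.

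**The case against.** The strongest reply is that this is an ambiguity in a minor analysis. SAP section 1 says the SAP is to be read together with the protocol. The PRO wording resembles the off-treatment seroclearance endpoints in section 5.3.1.1.1, which do require no NA restart. The analysis is exploratory, and section 9.1.2 leaves the time points to judgement.

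Part of this stands. The analysis is exploratory, and a careful programmer might go back to the protocol. But there is no cross-reference. The endpoints at 24 and 48 weeks after stopping are also timed from whenever treatment stopped, whereas the PRO subgroups are timed from Week 48. The SAP states a rule, and that rule differs from the protocol's.

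A reader might infer three stronger things that the documents do not support.

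- That relapsers in general would be counted as cured. The SAP labels the group by seroclearance, keeps functional cure as a separate term that excludes NA restart, and admits only re-treated participants who are HBsAg <LLOQ at the time point.
- That the off-treatment change is lost altogether. As shown above, its mean may be recoverable by subtraction. What is missing is the paired summary and its variability.
- That the trial's stated PRO question is the effect of cure on stigma and quality of life. The listed objective is the impact of study intervention during treatment and follow-up, and the comparison by seroclearance is one further look within it.

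**Conclusion.** The mismatch is real and applies to both PRO instruments. As written, SAP sections 9.1.2 and 9.2.2 would place participants who restarted NA and are HBsAg <LLOQ in the seroclearance group, and they omit a contrast the protocol specifies. The primary endpoint and error rate are unaffected.

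The size is unknown. Each such participant would be about 4% of a group of about 22, assuming the design rates hold and the arms are pooled. The textual finding does not depend on those assumptions.

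One gap lies in the protocol itself. Its comparator is participants without seroclearance, so someone with seroclearance after NA restart belongs to neither protocol group. Restoring the protocol's wording alone would leave that person unassigned.

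**What to change.** In SAP sections 9.1.2 and 9.2.2:

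1. Restore the no-NA-restart condition to the responder definition.
2. Keep the protocol's comparator, participants without HBsAg seroclearance at the time point, and state where participants with seroclearance after NA restart go. Showing them as a separate group would do.
3. Add descriptive change from Week 48 to each later scheduled PRO visit, at least Weeks 72 and 96, for the self-stigma scores, the EQ-5D VAS and the index, by responder group.

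If the omissions were intended, record them as departures from Protocol section 9.4.1.4 with the reason.

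The cost is SAP wording and one extra set of descriptive tables. No new data are needed.
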